10. SAFETY ANALYSES

All subjects who received study drug will be included in the safety analyses, analyzed according to the study treatment actually received.

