10.1 Adverse Events

All adverse event summaries will be restricted to Treatment Emergent Adverse Events (TEAE), which are defined as those AEs that occurred after dosing and those existing AEs that worsened during the study. Verbatim terms on case report forms will be mapped to preferred terms and system organ classes using the MedDRA dictionary (version 12.0).

Each adverse event summary will be displayed for the Safety population. Summaries that are displayed by system organ class and preferred terms will be ordered by descending order of incidence of system organ class and preferred term within each system organ class. Summaries of the following types will be presented:

- Subject incidence of TEAEs and total number of unique TEAEs by MedDRA system organ class and preferred term.
- Subject incidence of TEAEs by MedDRA system organ class, preferred term, and highest severity. At each level of subject summarization a subject is classified according to the highest severity if the subject reported one or more events. A

missing column will be added to the summary table if any TEAEs are reported with missing severity.

- Subject incidence of TEAEs by MedDRA system organ class, preferred term, and closest relationship to study drug (Related/Not Related). At each level of subject summarization a subject is classified according to the closest relationship if the subject reported one or more events. AEs with a missing relationship will be considered related for this summary.
- Subject incidence of serious TEAEs and total number of unique serious TEAEs by MedDRA system organ class and preferred term.
- Subject incidence of TEAEs and total number of unique serious TEAEs leading to discontinuation of study drug or premature withdrawal from study.
- Subject incidence of TEAEs reported after physical examination of injection site and safety review on Day 1 (for Treatment Regimen 2 only), Day 3 through Day 7 and Day 14 will be presented by injection type.

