Subjects Reporting at Least One Adverse Event	n (%)	n (%)	n (%)	n (%)	n (%)
System Organ Class 1	n (%)	n (%)	n (%)	n (%)	n (%)
Preferred Term 1	n (%)	n (%)	n (%)	n (%)	n (%)
Preferred Term 2	n (%)	n (%)	n (%)	n (%)	n (%)
.
System Organ Class 2	n (%)	n (%)	n (%)	n (%)	n (%)
Preferred Term 1	n (%)	n (%)	n (%)	n (%)	n (%)
Preferred Term 2	n (%)	n (%)	n (%)	n (%)	n (%)
.

[1] At each level of summation (overall, system organ class, preferred term), subjects reporting more than one adverse event are counted only once using the highest severity.
path\t_program.sas date time

Table
Treatment Emergent Adverse Events by System Organ Class and Relationship to Study Drug
Safety Population

System Organ Class / Preferred Term [1]	Safety Population (N=)	
	Related	Not Related
Subjects Reporting at Least One Adverse Event	n (%)	n (%)
System Organ Class 1	n (%)	n (%)
Preferred Term 1	n (%)	n (%)
Preferred Term 2	n (%)	n (%)
.		
System Organ Class 2	n (%)	n (%)
Preferred Term 1	n (%)	n (%)
Preferred Term 2	n (%)	n (%)

[1] At each level of summation (overall, system organ class, preferred term), subjects reporting more than one adverse event are counted only once using the closest relationship to study drug.
path\t_program.sas date time

Table 28
Treatment Emergent Serious Adverse Events by System Organ Class
Safety Population

System Organ Class / Preferred Term	Safety Population (N=)	
	Number of Subjects [1]	Number of Events
Subjects Reporting at Least One Serious Adverse Event	n (%)	n
System Organ Class 1	n (%)	n
Preferred Term 1	n (%)	n
Preferred Term 2	n (%)	n
.		
System Organ Class 2	n (%)	n
Preferred Term 1	n (%)	n
Preferred Term 2	n (%)	n

[1] At each level of summation (overall, system organ class, preferred term), subjects reporting more than one serious adverse event are counted only once.
path\t_program.sas date time

Table 29
Treatment Emergent Adverse Events Leading to Discontinuation of Study Drug or Premature Withdrawal of From Study Safety Population

System Organ Class / Preferred Term	Safety Population (N=)	
	Number of Subjects [1]	Number of Events
Subjects Reporting at Least One Serious Adverse Event	n (%)	n
System Organ Class 1	n (%)	n
Preferred Term 1	n (%)	n
Preferred Term 2	n (%)	n
.		
System Organ Class 2	n (%)	n
Preferred Term 1	n (%)	n
Preferred Term 2	n (%)	n

[1] At each level of summation (overall, system organ class, preferred term), subjects reporting more than one adverse event are counted only once.
path\t_program.sas date time

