					TR 1-1	TR 1-2	TR 1-3	TR 1-4	TR 1-1	TR 1-2	TR 1-3	TR 1-4
									None	None	None	None

path\t_program.sas date time

Listing 14 (cont.)
Study Drug Administration – Treatment Regimen 1
Part 3 of 4: Study Drug Administration

Subject	Visit	Treatment Date	TR 1-1		TR 1-2		TR 1-3		TR 1-4	
			Drug Injected?	Time						
No:reason										

path\t_program.sas date time

Listing 14 (cont.)
Study Drug Administration – Treatment Regimen 1
Part 4 of 4: Physical Examination and Safety Review after Injection

Subject	Visit	Treatment Date	Test Category	Asse. Time	AE #			
					TR 1-1	TR 1-2	TR 1-3	TR 1-4
			Physical Exam. (10 mins. Post) Safety Review (30 mins Post)	None	None	None	None	None

path\t_program.sas date time

Listing 15
Study Drug Administration – Treatment Regimen 2
Part 1 of 4: Physical Examination Prior to Injection

Subject	Visit	Subject Randomized?	Treatment Date	Asse. Time	ICDRG Score				AE #			
					TR 2-5	TR 2-6	TR 2-7	TR 2-8	TR 2-5	TR 2-6	TR 2-7	TR 2-8
									None	None	None	None

path\t_program.sas date time

Listing 15 (cont.)
Study Drug Administration – Treatment Regimen 2
Part 2 of 4: Study Drug Administration

Subject	Visit	Treatment Date	TR 2-5		TR 2-6		TR 2-7		TR 2-8	
			Drug Injected?	Time						
No:reason										

path\t_program.sas date time

Listing 15 (cont.)
Study Drug Administration – Treatment Regimen 2
Part 3 of 4: Physical Examination and Safety Review after Injection

Subject	Visit	Treatment Date	Test Category	Asse. Time	AE #			
					TR 2-5	TR 2-6	TR 2-7	TR 2-8
			Physical Exam. (10 mins. Post) Safety Review (30 mins Post)		None	None	None	None

path\t_program.sas date time

Listing 15 (cont.)
Study Drug Administration – Treatment Regimen 2
Part 4 of 4: Application of Nickel Sulfate Patches

Subject	Visit	Treatment Date	Application Time	Mark if Not Done	4 Patches	Not applied Reason	Concentrations of Nickel Sulfate
---------	-------	----------------	------------------	------------------	-----------	--------------------	----------------------------------

path\t_program.sas date time

Listing 16
Adverse Events

Subject	Mark if None	AE Term	Start Date/Time	Resolved Date/Time	Serious	Severity (CTCAE3)	Action Taken with Study Drug	Relationship to Study Drug	Other Action Taken	Outcome
---------	--------------	---------	-----------------	--------------------	---------	-------------------	------------------------------	----------------------------	--------------------	---------

path\t_program.sas date time

Listing 17

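### SAP 10.1 counts subjects for any TEAE that stops dosing but events only if serious, the table shell contradicts itself on the same point, and no table shows discontinuation by injection type.

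*SAP*

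**What the plan says.** Assessing the safety and tolerability of the rHuPH20 injection is a primary objective (Protocol 2.1, SAP 2).

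SAP 10.1 lists the AE summaries. The overall one is "Subject incidence of TEAEs and total number of unique TEAEs by MedDRA system organ class and preferred term", with the same scope for subjects and events. The serious-TEAE summary restricts both measures to serious events. The discontinuation summary alone mixes scopes: "Subject incidence of TEAEs and total number of unique serious TEAEs leading to discontinuation of study drug or premature withdrawal from study".

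The shell in SAP Appendix B is titled "Treatment Emergent Adverse Events Leading to Discontinuation of Study Drug or Premature Withdrawal of From Study". Its footnote says that "subjects reporting more than one adverse event are counted only once". Neither mentions seriousness, but the first row is "Subjects Reporting at Least One Serious Adverse Event". There is one Safety Population column, giving number of subjects and number of events, with no split by product or regimen.

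SAP 10 says subjects will be "analyzed according to the study treatment actually received". Protocol 8 says that all data, safety data included, are to be summarized by treatment group. Within each subject, two of the four regions in each regimen receive rHuPH20 and two receive placebo (Protocol 5.3.10).

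**The concern.** Discontinuation because of an adverse event is a direct sign of poor tolerability, and this is the only planned table of the events behind it. Protocol 5.3.17 requires every injection-site reaction to be recorded as an AE. Protocol 1.1 describes the commonest AEs so far as local, transient and self-limited, and such events would seldom meet the SAE definition in Protocol 7.1. If one of them did stop dosing, SAP 10.1 as worded would leave it out of the event count.

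SAP 5 also defines stopping for toxicity by the reason for not completing the study together with withdrawal of drug, and sets no seriousness condition. A subject could therefore be evaluable because of a toxicity stop that the discontinuation table records as zero events.

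The pooled column raises a separate question. Each subject receives both products, so a per-subject count cannot show whether the event behind a stop arose at an rHuPH20 site or a placebo site.

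**Working it through.** The plan states no figure to reproduce here: neither document gives a discontinuation rate, and the 20 evaluable subjects come with no derivation. The check compares the texts, followed by a literal count and an illustrative range.

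**1. Scope of each element**

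| Element | Subjects | Events |
|---|---|---|
| SAP 10.1, overall TEAE summary | all TEAEs | all TEAEs |
| SAP 10.1, serious-TEAE summary | serious | serious |
| SAP 10.1, discontinuation summary | all TEAEs | serious only |
| Discontinuation shell, title | all TEAEs | all TEAEs |
| Discontinuation shell, footnote | all AEs | not addressed |
| Discontinuation shell, top row | serious only | not stated |

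The top-row label recurs in Table 12, which reports TEAEs by regimen and injection type without regard to seriousness. That points to a label copied from the serious-AE shell.

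**2. Literal count.** Let k subjects stop for a non-serious event and s for a serious one, with one event each.
- SAP 10.1 as written: subjects = k + s; events = s.
- Top row, if its label is programmed literally: subjects = s.
- With *serious* removed from the event count and the label: subjects = k + s; events = k + s.

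Hypothetical values:
- k = 3, s = 0: 3 subjects and 0 events as written; 0 subjects in a literal top row; 3 and 3 after correction.
- k = 3, s = 1: 4 subjects and 1 event as written; 1 subject in a literal top row; 4 and 4 after correction.

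**3. How often the mismatch could appear.** Assume a proportion p of subjects with a non-serious stop; p is not in the documents. Expected number = N × p, and the chance of at least one = 1 − (1 − p)^N. N = 20 is the evaluable target and N = 30 the enrolment maximum.

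| p | N = 20: expected; chance of at least one | N = 30: expected; chance of at least one |
|---|---|---|
| 5% | 1; 64% | 1.5; 79% |
| 10% | 2; 88% | 3; 96% |
| 20% | 4; 99% | 6; 99.9% |

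At p = 0 nothing is lost.

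**4. Attribution.** Regimen 1 has 4 regions × 5 injections = 20. Regimen 2 has 4 × 6 = 24, including the pre-treatment. The total is 44 per subject, 22 of each product, so a single per-subject column cannot separate them.

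The other planned outputs carry part of the link:
- Table 12 gives subjects and events by injection type, but does not single out events that stopped dosing.
- Listings 14 and 15 give an AE number for each region, for example under "Part 4 of 4: Physical Examination and Safety Review after Injection".
- Listing 8 marks each region as rHuPH20 or placebo.
- Listing 16 gives seriousness and action taken, but its layout has no AE number or region. It has to be joined to Listings 14 and 15 on subject, AE term and time.

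**The case against.** The best reply is that this is a slip, not an analysis choice. The entry in the list of tables, the shell title and the footnote all cover adverse events in general, and the column is headed simply as number of events. A programmer could well follow these and ignore one stray word. That is plausible, but SAP 10.1 carries the word too, so text and shell need to be brought into line.

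A reader might infer that the summary counts only serious events altogether. It does not: SAP 10.1, the shell title and the footnote all put subjects with non-serious stops in the subject count. Only the event count is restricted, plus the top row if its label is taken literally.

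A reader might also infer that these events cannot be traced to rHuPH20 or placebo. With at most 30 subjects, Table 12 and Listings 8, 14, 15 and 16 allow it by hand. What is missing is a table that shows it and a direct key in Listing 16.

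Nor do the documents show that non-serious site reactions are the events most likely to stop dosing. Protocol 1.1 says they are the most common and self-limited, and Protocol 7.4 describes mild events as generally not requiring cessation.

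Finally, withdrawal from the study stops both products together, and a systemic event cannot be assigned to either. This stands: a split by product informs only for events localized to a site.

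**Conclusion.** The inconsistency is real. SAP 10.1 gives subjects and events different scopes in one summary, and the shell's first row contradicts its own title and footnote. Followed as written, each non-serious event that stops dosing adds nothing to the event count. The absence of any table crossing discontinuation with injection type is a smaller gap, limited to site-localized events.

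The size is unknown. The range under working rests on assumed rates, and the under-count is zero if no one stops for a non-serious event. No efficacy result depends on it. It is worth correcting because it bears on a primary safety and tolerability objective and costs little.

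**What to change.** - In the SAP 10.1 discontinuation bullet, delete *serious* from the event count, so that both measures cover all TEAEs leading to discontinuation or withdrawal.
- Delete *Serious* from the top-row label of the discontinuation shell (Table 11 in the list, Table 29 in the layouts) and of Table 12. Changing SAP 10.1 alone would leave both shells contradictory.
- Show the discontinuation table by rHuPH20 site, placebo site and not site-specific, using the per-region AE numbers already collected. The last column holds systemic events.
- Add AE number and region to Listing 16 so that it joins directly to Listings 14 and 15.

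The cost is small: wording changes, a few columns and some programming, with no new data. Cells will be sparse at this sample size, and systemic events will remain unattributable to one product.

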10.2 Vital Signs

Assessment of vital signs includes the measurement of blood pressure (systolic and diastolic), heart rate, and respiration rate and body temperature (at screening). Vital signs will be recorded one time at Screening; pre- and post injection vital sign results will be collected on the following days: Day 1, Day 3, Day 4, Day 5, Day 6, Day 7, Day 14.

Vital signs will be summarized using descriptive statistics at each visit time point. Changes from baseline will also be summarized. Baseline is defined as the pre-dose result for the visit under consideration.

10.3 Physical Examination

Physical examination results will be summarized with shift tables comparing baseline to the most abnormal post baseline assessment. Possible assessments for each body system include: Normal/Return to Normal and Abnormal.

Baseline will be defined as the last non-missing result recorded before injection.

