#### **4.4. Assessments**

- Complete medical history at screening
- Complete physical exam at screening
- A physical exam including visual inspection of the injection site at baseline, treatment days 3 – 7, and at follow-up visit
- A complete blood count (WBC with differential, Hgb, Hct, and platelets) at screening
- Vital signs Body Temperature (screening), BP, Heart Rate, Respiration Rate at screening, baseline, before each injection on treatment days 3 - 7, and within 10 minutes following each injection
- Pregnancy test at screening and baseline
- Targeted physical exam (positive findings on a review of systems and follow-up of findings from previous physical examinations) at baseline and treatment days 3 - 7
- Concomitant medications from 21 days before screening through the follow-up evaluation at 7-10 days after final injection
- TEWL (Trans-epidermal water loss) assessment at Baseline (Day 1) and treatment days 3 – 5
- Digital photographs of each allergen test site at Baseline (Day 1) and treatment days 3 – 5
- Chromometer images of each allergen test site at Baseline (Day 1) and treatment days 3 – 5
- Subject questionnaire at treatment days 3 - 5
- Adverse events / toxicity assessment at baseline through follow-up visit

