### **5.3.6. Targeted Physical Exam**

An abbreviated physical exam, reviewing only those body systems for which an abnormality was noted during the complete review of systems or a follow up of previous physical exam(s), will be performed by the Investigator prior to study drug injection at Visits 1-7, and at the Follow-up Visit.

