Table 12
Treatment Emergent Adverse Events by System Organ Class and Injection Type
Safety Population

System Organ Class / Preferred Term	Treatment Regimen 1 (N=)				Treatment Regimen 2 (N=)			
	rHuPH20		Placebo		rHuPH20		Placebo	
	Number of Subjects [1]	Number of Events	Number of Subjects [1]	Number of Events	Number of Subjects [1]	Number of Events	Number of Subjects [1]	Number of Events
Subjects Reporting at Least One Serious Adverse Event	n (%)	n	n (%)	n	n (%)	n	n (%)	n
System Organ Class 1	n (%)	n	n (%)	n	n (%)	n	n (%)	n
Preferred Term 1	n (%)	n	n (%)	n	n (%)	n	n (%)	n
Preferred Term 2	n (%)	n	n (%)	n	n (%)	n	n (%)	n
.								
System Organ Class 2	n (%)	n	n (%)	n	n (%)	n	n (%)	n
Preferred Term 1	n (%)	n	n (%)	n	n (%)	n	n (%)	n
Preferred Term 2	n (%)	n	n (%)	n	n (%)	n	n (%)	n

Note: For this summary, only Adverse Events reported during the physical examinations/safety reviews at Day 1 (TR 2 only), Day 3 through Day 7, and Day 14 are considered.

[1] At each level of summation (overall, system organ class, preferred term), subjects reporting more than one adverse event are counted only once.

path\t_program.sas date time

Table 31
Vital Signs
Safety Population

Vital Sign	Time Point	Safety Population (N=)
Systolic BP (mmHg)	Screening	
	N	n
	Mean (SD)	xx.x (xx.xx)
	Median	xx.x
	Min, Max	xx, xx
	Day 1 Pre-Injection	
	N	n
	Mean (SD)	xx.x (xx.xx)
	Median	xx.x
	Min, Max	xx, xx
	Day 1 Post-Injection	
	N	n
	Mean (SD)	xx.x (xx.xx)
	Median	xx.x
	Min, Max	xx, xx
	Day 1 Change from Baseline [1]	
	N	n
	Mean (SD)	xx.x (xx.xx)
	Median	xx.x
	Min, Max	xx, xx
	...	
Diastolic BP (mmHg)		

[1] Baseline is defined as pre-injection assessment for the visit under consideration.
path\t_program.sas date time

Programmer note: Table will include the following vital signs: systolic BP (mmHg), diastolic BP (mmHg), Heart Rate (bpm) and Respiration (breaths/min). for each vital sign, time points will include: Screening, Day 1 Pre-Injection, Day 1 Post-Injection, Day 1 Change from Baseline, Day 3 Pre-Injection, Day 3 Post-Injection, Day 3 Change from Baseline, Day 4 Pre-Injection, Day 4 Post-Injection, Day 4 Change from Baseline, Day 5 Pre-Injection, Day 5 Post-Injection, Day 5 Change from Baseline, Day 6 Pre-Injection, Day 6 Post-Injection, Day 6 Change from Baseline, Day 7 Pre-Injection, Day 7 Post-Injection, Day 7 Change from Baseline, Day 14.

Table 32
Physical Examination
Safety Population

Most Abnormal Post-Baseline Assessment	Safety Population (N=)	
	Normal	Abnormal
HEENT		

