Serious Adverse Events

Subject	Mark if None	AE Term	Start Date/Time	Resolved Date/Time	Severity (CTCAE3)	Action Taken with Study Drug	Relationship to Study Drug	Other Action Taken	Outcome
---------	--------------	---------	-----------------	--------------------	-------------------	------------------------------	----------------------------	--------------------	---------

path\t_program.sas date time

Listing 18
Vital Signs

Subject	Visit	Mark if Not Done	Not Done Reason	Visit Date	Category	Visit Time	Heart Rate (bpm)	Blood Pressure (mmHg)	Respiration (breaths/min)	Body Temperature (°F)
Screening										
	Day 1				Pre-injection					
					Post-injection					
	...									
	Day 14									

path\t_program.sas date time

Listing 19
Physical Examination

Subject	Visit	Mark if Not Done	Not Done Reason	Date of Exam	Any Change from Previous Exam	Body System	Result	Description of Abnormality
							Normal	
							Abnormal	
							Abnormal, Clinically Significant	

path\t_program.sas date time

Listing 20
Comments

Subject	Mark if None	Comment #	Pertains to Visit Date	CRF Page	Comment
---------	-----------------	-----------	---------------------------	----------	---------

path\t_program.sas date time

Listing 21
Prior and Concomitant Medications

Subject	Mark if None	CM #	Medication	Indication	Start Date	Stop Date	Dose	Unit	Route	Frequency	Taken for AE?	AE #
						ongoing						

path\t_program.sas date time

Listing 22
Deaths

Subject	Date of Death	Date Death Reported to Site	Primary Cause of Death	Was Autopsy Performed?	Comment	Signature of Investigator	Signature Date
---------	---------------	-----------------------------	------------------------	------------------------	---------	---------------------------	----------------

path\t_program.sas date time

Listing 23
Subject Visit

Subject	Initials	Visit	Visit Date
----------------	-----------------	--------------	-------------------

path\t_program.sas date time

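### The physical examination shift table has two result levels where Listing 19 has three, so worsening from Abnormal to clinically significant appears as no shift

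*SAP*

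**What the plan says.** SAP 10.3 sets the display: "Physical examination results will be summarized with shift tables comparing baseline to the most abnormal post baseline assessment". It then limits the categories: "Possible assessments for each body system include: Normal/Return to Normal and Abnormal". The layout in SAP Appendix B (Table 14 in the list of tables, headed Table 32 in the layouts) follows this. Under the label "Most Abnormal Post-Baseline Assessment" it crosses Normal/Abnormal with Normal/Abnormal for each body system, in one pooled Safety population.

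Listing 19 in SAP Appendix C gives three entries in its result column: Normal, Abnormal and "Abnormal, Clinically Significant" (CS below). Neither document says how CS is to be mapped to the two table categories.

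On baseline, 10.3 says: "Baseline will be defined as the last non-missing result recorded before injection".

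On what is examined, Protocol 5.3.5 places the complete examination at screening only. Later examinations are targeted. Protocol 5.3.6 describes the targeted examination as "reviewing only those body systems for which an abnormality was noted during the complete review of systems", and adds follow-up of earlier examinations. Protocol 4.4 words it differently: "Targeted physical exam (positive findings on a review of systems and follow-up of findings from previous physical examinations) at baseline and treatment days 3 - 7". Appendix A footnote d of the protocol agrees with 4.4.

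**The concern.** A table that promises the most abnormal post-baseline result needs a scale that can rank abnormal results. Two levels cannot place CS above Abnormal. A system that was Abnormal before dosing and CS afterwards therefore has the same baseline and worst value in the table, and the reader sees no change.

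Physical examination is a named basis of the safety objective (Protocol 2.2, SAP section 2), and this is the only planned summary table of body-system examination results. Because the full examination is not repeated after screening, post-dose data come mostly from systems already flagged. Such systems often start the shift at Abnormal, and from there CS is the only higher level. What is at stake is whether the summary can show a clinically significant deterioration in those systems.

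**Working it through.** The plan gives no figure to reproduce. The check is to list the transitions and map them through the rule in SAP 10.3.

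**Inputs**
- Levels in Listing 19: Normal (N) < Abnormal (A) < CS, so three levels and 3 x 3 = 9 baseline-by-worst cells.
- Levels in SAP 10.3 and the shell: two, so 2 x 2 = 4 cells.
- Mapping assumed: N to Normal, and both A and CS to Abnormal. The SAP does not state this, but it is the only assignment that fits the labels.

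**Worsening transitions on three levels:** (3 x 2) / 2 = 3.

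| Recorded transition | Cell in the planned table | What the reader sees |
|---|---|---|
| N to A | Normal to Abnormal | a shift |
| N to CS | Normal to Abnormal | a shift, same cell as N to A |
| A to CS | Abnormal to Abnormal | no shift |

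**Result:** 1 of 3 worsening transitions is hidden. The other 2 are visible but cannot be told apart. Of the 2 transitions that end in CS, 1 is hidden and 1 loses its grade. In a 3x3 table all 3 occupy separate cells.

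**Which transitions the targeted examination can reach**
- A system Abnormal at baseline and followed up: the only upward step is A to CS, which is hidden.
- A system abnormal at screening but back to normal on Day 1: 10.3 allows a return-to-normal result, and the Day 1 result becomes baseline. A later abnormality is a visible shift.
- A system normal at screening with a new positive on review of systems: Protocol 4.4 and Appendix A footnote d can be read as bringing it in. Its worsening is then visible too.

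The hidden transition is thus a main one for the targeted examination, but not the only one. These are counts of category transitions. The documents give no expected frequency for any of them.

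**The case against.** The strongest reply is that little is lost. Listing 19 keeps three levels, a change-from-previous column and a description for each subject, in a study of at most 30. SAP 10.1 counts existing adverse events that worsened as treatment-emergent and tabulates highest severity. Injection site reactions must be recorded as adverse events (Protocol 5.3.17). Every subject receives both products and the shell is pooled, so the table cannot compare treatments at either two or three levels. Two-level shift tables are also a common choice.

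Most of this stands and limits the consequence. The adverse event route is only a partial backstop. Protocol 7.3 tells investigators when an isolated laboratory abnormality must be reported as an adverse event, but no equivalent rule covers body-system examination findings. Protocol 7.7 sends events before first dosing to the medical history form, so a baseline finding is not clearly an existing adverse event that can worsen. Reporting then depends on judgement under the general definition.

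A second objection is that the CRF is not among the documents, so three post-baseline levels are inferred from a listing shell. Listing 19 draws on two CRF plates (6 and 10), and the return-to-normal option in 10.3 does not appear in Listing 19, so the forms may differ. This stands as a condition on the finding.

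Three stronger readings are tempting, and the documents do not support them:
- A reader might infer that any worsening to CS disappears. Normal to CS does show as a shift; only its grade is lost.
- A reader might infer that A to CS is the only worsening a targeted examination can find. Protocol 4.4, Appendix A footnote d and the return-to-normal option all allow others.
- A reader might take the baseline wording, with injections on Day 1 and Days 3 to 7, to mean that the Day 7 pre-dose result is baseline and only Day 14 is post-baseline. That would defeat the purpose of a worst post-baseline result. SAP 10.2 also says so explicitly when it wants a visit-specific baseline, and 10.3 does not. Before first dosing is the natural reading.

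**Conclusion.** The mismatch is real and confined to one table. As planned, the physical examination shift table hides 1 of 3 worsening transitions (Abnormal to CS) and merges the other 2. The hidden one matters in this design because post-dose examinations concentrate on systems already abnormal. The underlying data are not lost, since Listing 19 shows the levels by subject, and no formal comparison depends on the table.

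The conclusion assumes that CS is mapped to Abnormal and that the post-baseline CRF page offers CS. If CS can be entered only at screening, a post-dose worsening to CS would never be recorded as such, and the table would not be hiding it. The baseline wording needs clarification but is not a separate defect.

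**What to change.** 1. Confirm that the CRF page used for post-baseline examinations carries the clinically significant option.
2. If it does, replace the two categories in SAP 10.3 with the three of Listing 19, ordered Normal, Abnormal (not clinically significant), Abnormal CS. Make the shell a 3x3 shift of baseline against the most abnormal post-baseline result.
3. If it does not, state in 10.3 how a CS result at screening is mapped and keep the two-level table.
4. As a clarification, state that baseline is the last non-missing result before the first study drug injection.

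The cost is a few words in the SAP and one extra row and column per body system (9 cells instead of 4). No new data are needed if step 1 is confirmed. With at most 30 subjects many cells will be empty, which is acceptable in a descriptive safety table.
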